8.2. Withdrawal from the Study

- A participant may withdraw from the study at any time at his/her own request, or may be withdrawn at any time at the discretion of the investigator for safety, behavioral, compliance, or administrative reasons.
- If the participant withdraws consent for disclosure of future information, the sponsor may retain and continue to use any data collected before such a withdrawal of consent.
- If a participant withdraws from the study, he/she may request destruction of any samples taken and not tested, and the investigator must document this in the site study records.
- See the schedule of activities for data to be collected at the time of study discontinuation and follow-up and for any further evaluations that need to be completed.

8.3. Lost to Follow Up

A participant will be considered lost to follow-up if he or she repeatedly fails to return for scheduled visits and is unable to be contacted by the study site.

The following actions must be taken if a participant fails to return to the clinic for a required study visit:

- The site must attempt to contact the participant and reschedule the missed visit as soon as possible and counsel the participant on the importance of maintaining the assigned visit schedule and ascertain whether or not the participant wishes to and/or should continue in the study.

- Before a participant is deemed lost to follow up, the investigator or designee must make every effort to regain contact with the participant (where possible, 2 telephone calls, and if necessary, a certified letter to the participant's last known mailing address or local equivalent methods). These contact attempts should be documented in the participant's medical record.
- Should the participant continue to be unreachable, he or she will be considered to have withdrawn from the study with a primary reason of lost to follow-up.

9. Study Assessments and Procedures

- Study procedures and their timing are summarized in the schedule of activities (Section 2.1 [Part A] and Section 2.2 [Part B]).
- Protocol waivers or exemptions are not allowed.
- Immediate safety concerns should be discussed with the sponsor immediately upon occurrence or awareness to determine if the participant should continue or discontinue study treatment.
- Adherence to the study design requirements, including those specified in the schedule of activities, is essential and required for study conduct.
- All screening evaluations must be completed and reviewed by the investigator or qualified designee to confirm that potential participants meet all eligibility criteria. The investigator will maintain a screening log to record details of all participants screened and to confirm eligibility or record reasons for screening failure, as applicable.
- Procedures conducted as part of the participant's routine clinical management (eg, blood count) and obtained before signing of the ICF may be utilized for screening or baseline purposes provided the procedure met the protocol-specified criteria and were performed within the time frame defined in the schedule of activities.
- Repeat or unscheduled blood samples may be taken for safety reasons or for technical issues with the samples.

Diagnostic Assessments

The SCID will be administered during the screening interviews by a psychiatrist, doctoral-level clinical psychologist, or other clinician who has extensive professional training and experience in the diagnosis of mental illness and who meets the training requirements and qualification standards set by the sponsor and rater training vendor.

9.1. Efficacy Assessments

The efficacy assessments (MADRS and CGI-S) will be administered by a psychiatrist, doctoral-level clinical psychologist, or other clinician who has extensive professional training and experience in the diagnosis of mental illness and who meets the training requirements and qualifications standards set by the sponsor and rater training vendor. Efficacy assessments will be performed as specified in the schedule of activities in Section 2.1 (Part A) and Section 2.2 (Part B).

9.1.1. Diagnostic Assessments

For Part A and Part B, the SCID will be administered during the screening interviews by a psychiatrist, doctoral level clinical psychologist, or other clinician who has extensive professional training and experience in the diagnosis of mental illness and who meets the training requirements and qualifications standards set by the sponsor and rater training vendor.

9.1.2. The Montgomery-Åsberg Depression Rating Scale

The MADRS ([Montgomery and Åsberg 1979](#)) is a clinician-rated scale ([Appendix 8](#)). The MADRS will be used to assess depressive symptomatology. Participants are rated on 10 items to assess feelings of sadness, lassitude, pessimism, inner tension, suicidality, reduced sleep or appetite, difficulty concentrating, and lack of interest. Each item will be scored on a 7-point scale. A score of 0 indicates the absence of symptoms, and a score of 6 indicates symptoms of maximum severity.

A qualified rater (ie, who meets the training requirements and qualifications set by the rater training vendor) at each investigational center will conduct the MADRS assessment.

For Part A, at Screening (Visit 1) and Visit 2 (predose), the MADRS will be administered with a look-back timeframe of 1 week. At all other evaluations, the MADRS will be administered with a look-back timeframe of “since last evaluation.”

For Part B, at Visit 1 (Screening) and Visit 2 (Day –1, baseline), the MADRS will be administered with a look-back timeframe of 1 week. At all other evaluations, the MADRS will be administered with a look-back timeframe of “since last evaluation.”

MADRS assessments will be performed as specified in the schedule of activities in Section [2.1](#) (Part A) and Section [2.2](#) (Part B).

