5.1.2. Part B

Part B of this study will include a total of 14 visits and will be approximately 5 weeks in duration as described below.

- Up to a 2-week screening period
- 2-week double-blind treatment period (Week 1 inpatient, Week 2 outpatient)
- 1-week outpatient safety follow-up period

Approximately 120 participants are planned for randomization in the double-blind treatment period (40 placebo participants, 40 AGN-241751 3 mg participants, 40 AGN-241751 25 mg participants). Eligible participants will be randomized in a ratio of 1:1:1 to one of 3 double-blind oral administration treatment groups: 3 mg dose of AGN-241751, 25 mg dose of AGN-241751, or placebo, administered BID. Participants who enrolled (were randomized) in Part A will not be permitted to screen into Part B (and vice versa).

Screening Period

After providing written consent, participants will enter a screening period of up to 14 days. Screening procedures may be conducted on up to 2 separate dates where necessary to accommodate participant and site schedule; however, every effort should be made to conduct all procedures as early as possible in the screening period. Participants will wash out of any ADT and prohibited medications under the supervision of the study investigator staff during the screening period. At Visit 2 (Day -1), study procedures required to determine eligibility will be completed prior to admission to the clinic. Participants meeting the eligibility criteria at Visit 2 (Day -1, Baseline) will be admitted to the inpatient facility, and the remainder of the Visit 2 study procedures will be completed. A urine pregnancy test should be done on Day -1 (at baseline), if more than a week has passed since the serum pregnancy test was done at Screening. Participants are required to not use any nicotine substances 1 hour prior to administration of the HVLT-R.

Double-Blind Treatment Period

Participants will be randomized in a ratio of 1:1:1 to 1 of 3 treatment groups (AGN-241751 3 mg BID, AGN-241751 25 mg BID, or placebo BID) for the 2-week double-blind treatment.

Participants will be administered 1 tablet in the morning and 1 tablet in the afternoon. At Visit 3 (Day 1), the participant will be randomized and assigned a treatment by the interactive web response system (IWRS), and the 1st dose of study medication will be administered in the morning after all predose assessments have been completed.

Week 1 Inpatient Double-Blind Treatment Period

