- It is expected that participants in the double-blind treatment period will remain inpatient during the 1st week (Visit 2 to Visit 10/Discharge).
- During the inpatient treatment period, participants will have 7 visits (Visits 3 to 9); each visit will occur daily with no visit windows.
- At Visit 3 (Day 1) during the predose evaluation period, if there is a significant change (worsening or improvement in depressive symptoms) from the baseline Visit 2 (Day -1) MADRS based on the judgment of the PI, a MADRS assessment should be performed prior to the 1st dose of study medication.
- Participants will be discharged at Visit 10 (Day 8) after all predose assessments, morning dosing, and 4-hour postdose assessments are completed.
- During the inpatient treatment period, predose assessments will be performed prior to morning dosing at all inpatient visits (Visit 3 through Visit 10). Postdose assessments will be performed, as follows:
 - Visit 3 to Visit 6: 1, 2, 4, 8, and 12 hours after the morning dose (\pm 20 minutes)
 - Visit 7 to Visit 9: 4, 8, and 12 hours after the morning dose (\pm 20 minutes)
 - Visit 10: 4 hours after the morning dose (\pm 20 minutes)
- Within each timepoint, multiple assessments will be performed, as follows:
 - Assessments should be performed within \pm 20 minutes of each other
 - All psychiatric assessments (Likert Patient Depressive Symptom Scales, CSSR-S, MADRS, and CGI-S) are to be completed first prior to any other assessments (ie, qEEG, ERP) within the timepoint.
 - Participants are required to not use any nicotine substances 1 hour prior to administration of the HVLT-R.
- The afternoon dose of study medication is to be administered 8 hours (\pm 1 hour) after the morning dose.

[figure not shown]
Week 2 Outpatient Double-Blind Treatment Period

- During the outpatient treatment period, there will be 2 visits conducted every 3 days (Visit 11 [Day 11] and Visit 12 [Day 14/ET]). If necessary, these study visits may be conducted up to 1 day before or after the scheduled visit day.
- All participants who receive study medication should complete Visit 12 (Day 14/ET)
- At Visit 10 (Day 8) prior to discharge, the participant will be dispensed Bottle 2 of study medication (refer to Section 7.1.2 for dosing instruction). Participants will be instructed to bring the study medication bottle to Visit 11 for the site staff to confirm dosing compliance

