6.1. Inclusion Criteria

Participants are eligible to be included in the study only if all of the following criteria apply. Inclusion criteria apply to Parts A and B unless otherwise noted.

1. Written informed consent from the participant has been obtained prior to any study-related procedures (as described in [Appendix 3](#)).
2. Male or female participants must be 18 to 65 years of age, inclusive, at the time of signing the informed consent.
3. Meet DSM-5 criteria ([American Psychiatric Association 2013](#)) for MDD (based on confirmation from the modified SCID), with a current major depressive episode of at least 8 weeks and not exceeding 18 months in duration at Visit 1.
4. Have a minimum score of 26 on the rater-administered MADRS at both Screening (Visit 1) and Visit 2 (Day 1 in Part A and Day –1 [Baseline] in Part B).
5. Have a CGI-S score ≥ 4 at both Screening (Visit 1) and Visit 2 (Day 1 in Part A and Day –1 [Baseline] in Part B).
6. Part A: Have a negative serum β -human chorionic gonadotropin (β -hCG) pregnancy test at Screening (Visit 1) if a WOCBP. Part B: If a WOCBP, have a negative serum β -hCG pregnancy test at Screening (Visit 1) AND a negative urine pregnancy test on Day –1 (baseline), if more than a week has passed since the serum pregnancy test at Screening. If urine pregnancy test is positive on Day –1, then a serum β -hCG pregnancy test should be done for confirmation.
7. Female participants willing to minimize the risk of becoming pregnant for the duration of the clinical study and follow-up period. A female participant is eligible to participate if she is not pregnant, not breastfeeding, and at least one of the following conditions applies:
 - a. Not a WOCBP

OR

 - b. A WOCBP who agrees to follow the contraceptive guidance in [Appendix 5](#) during the treatment period and for at least 4 to 5 weeks after the last dose of study treatment.

8. Male participants willing to minimize the risk of inducing pregnancy for the duration of the clinical study and follow-up period. A male participant must agree to use contraception as detailed in [Appendix 5](#) of this protocol during the treatment period and for at least 10 weeks after the last dose of study treatment and refrain from donating sperm during this period.
9. Able, as assessed by the investigator, and willing to follow study instructions and likely to complete all required study visits.

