Dosing Instructions (Part B)	
Starting with inpatient Visit 3 (Day 1; after the participant has been in the inpatient unit since the previous day), participants will be administered 1 tablet in the morning and 1 tablet in the afternoon from Bottle 1 after all predose assessments have been completed. From Days 2 to 7 inpatient, each day the site staff will give the participant 1 tablet in the morning and 1 tablet in the afternoon at 8 hours (\pm 1 hour) after the morning dose, administered from Bottle 1.
 
At Visit 10 (Day 8) prior to discharge, the participant will be dispensed Bottle 2 of study treatment and will be instructed to each day take 1 tablet in the morning and 1 tablet in the afternoon at 8 hours (\pm 1 hour) after the morning dose. Participants will also be instructed to bring the unused study treatment to Visits 11 and 12 for the site staff to confirm dosing compliance.
 
A Patient Diary containing a Study Medication Dosing Log will be provided at Visits 10 and 11 for completion by the participant at home. Participants will be instructed by site staff to record the date and time of the Visit 10 (Day 8) afternoon dose and each subsequent dose taken (morning and afternoon) at home, inclusive of doses on days when the participant has a clinic visit (Visit 11 and Visit 12/ET).
	Same as for active treatment

Study Treatment Name	AGN-241751	Placebo
	At Visits 11 and 12, the participant will return the diary provided at the prior visit. Site staff will review the diary to confirm compliance and proper completion of the diary. At Visits 11 and 12, prior to leaving the clinic, the participant will be given a new diary.	
Packaging and Labeling	Allergan will provide double-blind study treatment in the form of identically appearing tablets containing AGN-241751 doses of 3 mg, 25 mg, or placebo.	Allergan will provide double-blind study treatment in the form of identically appearing tablets containing AGN-241751 doses of 3 mg, 25 mg, or placebo.
Manufacturer	Allergan, Inc.	Allergan, Inc.

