10.3.1.1.2. Part B

The primary and secondary efficacy endpoints are listed below and analyses will be defined in the following sections. All analyses for other efficacy endpoints listed below will be defined in more detail in the SAP for Part B.

Primary efficacy endpoint for Part B of the study:

- Change from baseline in MADRS at 7 days after first dose of treatment

Secondary efficacy endpoint for Part B of the study:

- Change from baseline in MADRS total score at Day 2, Day 11, Day 14, Day 18, and Day 21, 7 days after the completion of AGN-241751 BID dosing

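### In Part B, unless the conditional Day 1 predose MADRS is done, the Day 2 MADRS looks back to Day -1, so about 40-50% of its recall window (on assumed clock times) precedes the first dose and the Day 2 effect may be attenuated.

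*Protocol*

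**What the plan says.** Protocol 9.1.2 sets the MADRS look-back. For Part B at Visit 1 and Visit 2 (Day -1), "the MADRS will be administered with a look-back timeframe of 1 week". For every later rating the rule is: "At all other evaluations, the MADRS will be administered with a look-back timeframe of “since last evaluation".

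The Visit 2 rating decides eligibility. Section 6.1 requires participants to "Have a minimum score of 26 on the rater-administered MADRS at both Screening (Visit 1) and Visit 2", and section 5.1.2 says that on Day -1 "study procedures required to determine eligibility will be completed prior to admission to the clinic". Dosing starts on the morning of Day 1, "after the participant has been in the inpatient unit since the previous day" (section 7.1.2).

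One MADRS may fall between Day -1 and the first dose. Section 5.1.2 and footnote g of the Part B schedule make it conditional: "if there is a significant change (worsening or improvement in depressive symptoms) from the baseline Visit 2", in the investigator's judgment, then "a MADRS assessment should be performed prior to the 1st dose of study medication". The next MADRS in the schedule is at Visit 4 (Day 2), apparently in the predose column.

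Section 10.3.1.1.2 lists as secondary endpoint: "Change from baseline in MADRS total score at Day 2, Day 11, Day 14, Day 18, and Day 21". The objectives in 4.2 call these time points key secondary.

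**The concern.** A Day 2 score is meant to show the patient's state about one day into treatment. If its recall period starts on Day -1, it also covers the rest of that day and a whole night before any drug was given. That time is untreated in every arm. Whatever weight a rater gives it pulls each arm toward baseline and reduces a true early difference between drug and placebo.

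The same visit also has two recall periods. A participant who had the conditional Day 1 rating is scored on time after the first dose only, and a participant who did not is scored on a mixture. The investigator's judgment on Day 1 decides which.

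The Day 2 rating is the earliest postdose MADRS in Part B. It feeds the Day 2 change score, the Day 2 responder and remitter rates, and the times to first response and remission (section 10.3.1.3.2). Rapid onset is a stated expected benefit of the compound (section 3.3).

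**Working it through.** The plan states no figure on this point, so there is nothing to reproduce.

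**Step 1. The window from the text.**
- Start: the Day -1 MADRS, on the calendar day before dosing (5.1.2, 7.1.2). No clock time is given.
- First dose: the morning of Day 1 (5.1.2). No clock time is given.
- End: the Day 2 MADRS, about 24 hours after the first dose. The schedule table is broken in the text available. The predose placement is read from alignment with the C-SSRS row, which 9.4.5 says is done predose.
- Reset: none. No text moves the start of the look-back to the first dose.

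**Step 2. The share before dosing.** Let P be the hours from the Day -1 rating to the first dose, and D the hours from the first dose to the Day 2 rating. The predose share is P / (P + D). All clock times are assumptions. The first three rows take dosing and the Day 2 rating at 08:00.

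| Day -1 rating | P | D | Predose share |
|---|---|---|---|
| 08:00 | 24 | 24 | 24/48 = 50% |
| 12:00 | 20 | 24 | 20/44 = 45% |
| 16:00 | 16 | 24 | 16/40 = 40% |
| 17:00, dose and Day 2 rating at 08:00 | 15 | 24 | 15/39 = 38% |
| 07:00, dose at 09:00, Day 2 rating at 08:00 | 26 | 23 | 26/49 = 53% |
| Conditional Day 1 predose rating done | about 0 | about 24 | about 0% |

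The last two timed rows are the extremes of a wider set of assumed times. If the Day 2 rating were made later in the day, with the Day -1 rating and the first dose both at 08:00, the share would be 24/52 = 46% at 12:00 and 24/60 = 40% at 20:00.

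**Step 3. The effect on the measured difference.** Let w be the weight that the rater gives to predose time, and δ the true difference after dosing, taken as constant. Predose time has an expected difference of zero, so the measured difference is (1 - w)δ.
- If the rater scores only the most recent state, w = 0 and nothing is lost.
- If the rater weights by time, w is 0.40 to 0.50, and 60% to 50% of δ remains.

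Appendix 8 gives some reason to expect w above zero. Duration is among the rating criteria for reported sadness and inner tension, and one item rates sleep. Of the two nights in the window, one precedes the drug.

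**Step 4. Which endpoints are touched.**
- Part A: the baseline is predose on Day 1 and the next rating is on Day 2, so the window is about 24 hours and all after dosing.
- Part B, Day 7 (primary): the previous MADRS is on Day 2, so the window is wholly on treatment.
- Part B, Day 2: the only MADRS time point affected.

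**Step 5. Baseline when the conditional rating is done.** Section 10.3.1 takes the last nonmissing efficacy assessment before the first dose, which would be the Day 1 rating. Section 10.3.1.3.2 names the Day -1 value as baseline for the additional parameters, which include MADRS response. The two differ for exactly these participants.

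**The case against.** The strongest objection is that the term evaluation is not defined. It could mean the last MADRS, or the last visit at which the patient was assessed. A predose assessment does take place on Day 1: the C-SSRS is done, and the investigator must judge whether depression has changed. Rater training material, which is not among the documents, might settle the start of the window. This stands as far as it goes. It makes the wording ambiguous, and that is itself a reason to fix it.

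Second, Part B is described as exploratory with no power basis (10.1.2), and Day 2 is one of five key secondary time points. That is correct and limits the weight of the point.

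Third, the mixed windows should not bias the comparison between arms. The conditional rating is triggered before dosing in a double-blind trial, so both window types should be balanced in expectation. That also stands. The effect is in one direction only: a true difference can shrink or stay the same.

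A reader might infer more than the documents support:
- That the effect is diluted. The size depends on rater weighting and speed of onset, and neither is given.
- That most participants are affected. The frequency of the conditional rating is not stated.
- That Day 2 MADRS is the only early efficacy measure. CGI-S by visit, time to first response and the Likert scales also address early change.
- That power collapses. With 40 per arm, a two-sample t-test at two-sided 5% and an assumed standardized effect of 0.50, power is 60%. It is 26% at 0.6 × 0.50 = 0.30 and 20% at 0.5 × 0.50 = 0.25. The effect size, the time-weighting and the t-test in place of the planned MMRM are all assumptions, so this is not a property of the plan.

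**Conclusion.** The point holds in a limited form. Read as the last MADRS, the Part B look-back rule puts about 40-50% of the Day 2 recall window before the first dose for any participant without the conditional Day 1 rating. The share is 38-53% over a wider set of assumed times. The possible loss of Day 2 effect runs from none to about half. The range rests on assumed clock times, a constant effect from the first dose, and rater weighting between most recent state and time average.

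It is also a matter of consistency, since one endpoint is collected over recall periods of about 24 or up to about 48 hours. It does not threaten the Day 7 primary and does not favor the drug. The correction is worth making because it is specific and cheap.

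**What to change.** In 9.1.2 and the rater instructions, state that for Part B at Visit 4 (Day 2) the MADRS look-back is since the first dose of study treatment, for all participants. Keep the present rule from Visit 9 (Day 7) onward.

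Reconcile 10.3.1 with 10.3.1.3.2, so that one rule says whether the Day -1 or the conditional Day 1 value is the baseline when both exist.

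The conditional Day 1 rating should not be given a one-week look-back to match Visit 2. It exists to capture change since Day -1. With time-weighting over seven days, one day would count for about 1/7 = 14%, so the re-rating would largely repeat the Day -1 score.

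The cost is one sentence on the look-back and one on the baseline, with no added visit or rating. The small downside is that the Day 2 recall period becomes about 24 hours against one week at baseline, as it already is in Part A.
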